9.10 Continuous glucose measurement

The CGM sensor has an in-use period of 7 days. The sensor will automatically stop recording data exactly 7 days after sensor insertion and start. This should be taken into account when scheduling the subjects' visits.

It is of utmost importance that the CGM sensor is calibrated regularly to ensure accuracy and for continuous reception of sensor glucose data. CGM sensor should be calibrated twice daily as per the manufacturer's instructions. Investigator or delegated staff should review the subject's diary to ensure that the CGM sensor is calibrated as required otherwise the subject should be re-trained.

Subjects should be instructed to avoid medications with acetaminophen/paracetamol while wearing the CGM sensor. These medications may affect the performance and readings of the CGM sensor (e.g. false high CGM readings) ⁷⁻⁹. Also, subject should be instructed to remove the Dexcom G5 sensor, transmitter, and receiver before x-ray, Magnetic Resonance Imaging (MRI), Computed Tomography (CT) scan, or high-frequency electrical heat (diathermy) ⁹.

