9.11 Self-measured plasma glucose

Subjects will be provided with a BG meter including auxiliaries as well as instructions for use. The subjects will be instructed in how to use the device and the instruction should be repeated, if needed

The BG meters use test strips calibrated to plasma values. Therefore, all measurements performed with capillary blood are automatically calibrated to plasma equivalent glucose values, which will be shown on the display.

The BG meter provided by Novo Nordisk should be used for the measurements required in the protocol. SMPGs must be performed to calibrate the CGM sensor (section [9.10](#)) and in the event of hypoglycaemic episode ([Appendix 7](#)) and should be reported in the diary, see section [9.14](#).

All SMPGs values must be recorded in the paper diary. In addition to paper diary, SMPGs performed for the calibration of the CGM sensor must also be recorded on the StudyPhone with CGM app. The record of each SMPG value on paper diary should include date, time and value. All data from the diary must be transcribed into the CRF during or following the contact.

9.12 iLet™ settings

The glucose target for the iLet™ will be set to 120 mg/dL (6.6 mmol/L). Subjects must be instructed not to change any settings related to BW and glucose target on the iLet™. Temporary targets are not allowed.

Initialisation of iLet™

The iLet™ should be initialised by entering the subject's current BW at visit 2 and visit 3. See section [9.4.1](#) for reporting of BW.

The date and time when the site staff starts the iLet™ at visit 2 and visit 3 will be considered as the time-point for initiation of treatment. This start date and time must be recorded in the CRF.

Stopping of iLet™

The date and time when the site staff stops the iLet™ at visit 3 and visit 4 will be considered as time-point for end of treatment. These stop date and time must be recorded in the CRF.

t_{max} setting

The t_{max} setting in the iLet™ should be set by the site staff at visit 2 and visit 3 as per the subject's randomisation sequence.

Meal announcements

Meal announcements can be entered via a user interface that runs on the iLet™. The user interface allows optional meal announcements, designated as “start of the day”, “middle of the day”, or “end of the day” or “sleeping”, of size “tiny”, “small”, “typical for me” or “large”. Subjects will be recommended to use this feature immediately before eating the main meals of the day, but not snacks.

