If the severity of a hypoglycaemic episode worsens, only one hypoglycaemic episode should be reported, reflecting the most severe degree of hypoglycaemia.

Investigator must instruct subjects that the answer to the question: "Was the subject able to treat him/herself?" must be answered "No" for an episode requiring assistance of another person to actively administer carbohydrate, glucagon, or take other corrective actions. PG concentrations may not be available during an event, but neurological recovery following the return of PG to normal is considered sufficient evidence that the event was induced by a low PG concentration²⁰.

Additional information (e.g. description of symptoms, alleviation of symptoms, seizure, coma, fatal) in relation to these severe hypoglycaemic episodes must be recorded.

Oral carbohydrates must not be given if the subject is unconscious.

The investigator must review the diary for low SMPG values not reported as hypoglycaemic episodes. The subject must be questioned whether any of the low values were severe, i.e. whether the subject was able to self-treat or not. If the subject was not able to self-treat, it has to be reported as a severe hypoglycaemic episode.

For low SMPG values for hypoglycaemic episodes where the subject was able to self-treat: If a hypoglycaemic episode form is not completed within 7 calendar days of the SMPG measurement, the episode should be reported on a hypoglycaemic episode form with as much information as possible. Novo Nordisk will not query for additional data except for the start date, SMPG value and whether the subject was able to self-treat due to decreased validity of such data^{[21, 22](#)}.

The subject must be re-trained in how to report hypoglycaemic episodes if the investigator identifies low SMPG values not reported as hypoglycaemic episodes.

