Subjects should be instructed to avoid medications with acetaminophen/paracetamol while wearing the CGM sensor. These medications may affect the performance and readings of the CGM sensor (e.g. false high CGM readings)⁷⁻⁹. *If a subject inadvertently takes acetaminophen during the trial, they will be instructed to contact study staff. Site staff will closely monitor their CGM readings and instruct the subject to measure BG using the BG meter to verify CGM readings as frequently as needed. If the BG is closely correlated with the subject’s CGM glucose, study staff will continue to monitor closely. If CGM glucose is consistently higher than BG by >20 mg/dL(1.1 mmol/L) for BG ≤100 mg/dL (5.55 mmol/L) or >20% for BG >100 mg/dL(5.55 mmol/L), then the study staff may temporarily discontinue the iLet™ for the duration of action of the acetaminophen.*

Also, subject should be instructed to remove the Dexcom G5 sensor, transmitter, and receiver before x-ray, Magnetic Resonance Imaging (MRI), Computed Tomography (CT) scan, or high-frequency electrical heat (diathermy).

Section 9.13: Back-up Kits

- ~~Fiasp® FlexTouch® pen injector (supplied by Novo Nordisk)~~
- ~~Needles (to be used with Fiasp® pen injector FlexTouch®)~~
- ~~Urine sticks for ketone monitoring~~

Subjects will also be encouraged to always carry the BG - meter, *Ketone meter* and test strips.

Section 9.15: Discharge criteria

The discharge of subjects from the “in-patient” period (during which subjects will be at a designated place such as a hotel) is at the discretion of the PI. In order to make the evaluation whether it is safe for the subjects to continue to the “out-patient” period of the trial, the PI may rely on data that include but are not limited to: hypoglycaemic episodes, the number of times carbohydrates are taken by subjects to prevent or treat hypoglycaemic episodes and time in low interstitial glucose (defined as < 54 mg/dL; 3 mmol/L). *Subjects will not be discharged if they have any severe hypoglycaemic episode possibly/probably related to investigational medicinal product and/or investigational medical device in the last 24 hours.*

In the event of diabetic ketoacidosis or ≥ 2 episodes of severe hypoglycaemia, possibly/probably related to investigational medicinal product and/or investigational medical device, the subject will discontinue the trial treatment as per section 8.1.

Section 9.16: Remote Monitoring

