Date:	21 January 2019
Version:	1.0
Status:	Final
Page:	1 of 4

Novo Nordisk

Protocol Amendment

no 4

**to Protocol, version 4
dated *19 Dec 2018***

Trial ID: NN1218-4360

**An Exploratory Trial investigating the Safety and Efficacy of Fast-acting Insulin Aspart in a
Closed-loop Insulin Delivery System (bionic pancreas) in Adults with Type 1 Diabetes**

**Trial phase: 2
Applicable to *all countries***

~~This confidential document is the property of Novo Nordisk. No unpublished information contained herein may be disclosed without prior written approval from Novo Nordisk. Access to this document must be restricted to relevant parties.~~

Table of Contents **"Double click to update Table of Content"**

1	Introduction including rationale for the protocol amendment.....	3
2	Changes	3

1 Introduction including rationale for the protocol amendment

In this trial the subjects will be using a blood glucose (BG) meter that has the capacity to store the date, time and values of all BG measurements taken in course of the trial. This data can be downloaded to the site computer at the site.

Following discussions at the investigator meeting, the sponsor and the investigator are in agreement that the data downloaded from the BG meter is a more accurate representation of the glucose values measured during the trial, than a collection of the data entered by the subjects in the subject diary, as the latter is a source to potential human error.

Hence, this amendment aims to modify the way of recording BG values used for CGM calibration in the subject's diary. The subject diaries will be modified to include only the date and time of the twice daily CGM calibrations performed by the subjects. This subject-entered time will be considered the approximate time, and will be used by the site staff to identify the corresponding actual time and glucose values in the downloaded BG meter data. Only the accurate dates, times, and values for CGM calibrations from the BG meter download will be entered into the CRF by the site staff. As a consequence, the subject will not be asked to correct the diary entries in case of a discrepancy with the BG meter download.

In this protocol amendment:

- Any new text is written *in italics*.
- Any text deleted from the protocol is written using ~~strike through~~.

2 Changes

Section 9.11 Self-measured plasma glucose

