Subjects will be provided with a BG meter including auxiliaries as well as instructions for use. The subjects will be instructed in how to use the device and the instruction should be repeated, if needed

The BG meters use test strips calibrated to plasma values. Therefore, all measurements performed with capillary blood are automatically calibrated to plasma equivalent glucose values, which will be shown on the display.

The BG meter provided by Novo Nordisk should be used for the measurements required in the protocol. SMPGs must be performed to calibrate the CGM sensor (section 9.10) and in the event of hypoglycaemic episode (Appendix 7) and should *for the latter* be reported in the diary, see section 9.14.

~~All SMPGs values must be recorded in the paper diary. In addition to paper diary, SMPGs performed for the calibration of the CGM sensor must also be recorded on the StudyPhone with~~

~~CGM app. The record of each SMPG value on paper diary should include date, time and value. All data from the diary must be transcribed into the CRF during or following the contact.~~

The subjects should use the SMPG values for the calibration of the CGM sensor by entering the measured values into the StudyPhone with CGM app. The record of these calibrations on paper diary should include date and time. The subjects must be instructed to bring the BG meters to the site at every site visit. The site will download the BG meter data at every site visit. Further the site will use the date and time reported by the subjects in the diary to identify the correct date, time and value in the data downloaded from the BG meter and report these in the CRF.

Documentum ObjectID : 

This is a representation of an electronic record that was signed electronically and this page is the manifestation of the electronic signature.

Document signed by:

Initials	Full Name	Date and Time of Signature (Server Time)
Meaning

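### Amendment 4 moves calibration SMPG values out of the diary, but Appendix 7 still names only the diary for the search for unreported low values

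*Combined protocol and SAP*

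**What the plan says.** Protocol version 2.0, Section 9.11, set the rule "All SMPGs values must be recorded in the paper diary", each with date, time and value. Appendix 7 makes every plasma glucose value at or below 3.9 mmol/L (70 mg/dL) reportable as a hypoglycaemic episode, with no exception for calibration readings. It then adds a safeguard: "The investigator must review the diary for low SMPG values not reported as hypoglycaemic episodes". For each value found, the subject is asked whether self-treatment was possible, and is re-trained in reporting.

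Protocol Amendment 4 strikes the Section 9.11 rule. Its rationale states: "The subject diaries will be modified to include only the date and time of the twice daily CGM calibrations performed by the subjects". The new Section 9.11 text agrees: "The record of these calibrations on paper diary should include date and time". Of the two SMPG purposes named there, calibration and hypoglycaemic episodes, only the second is still reported in the diary. The calibration readings take another route: "The site will download the BG meter data at every site visit", and according to the rationale the "values for CGM calibrations from the BG meter download will be entered into the CRF by the site staff".

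Section 9.11 is the only section that Amendment 4 lists as changed. The changes listed in Amendments 1 to 3 do not touch the Appendix 7 sentence either.

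**The concern.** The Appendix 7 review exists to catch low readings that the subject did not report. It could do so while the diary held every reading. After Amendment 4, the only SMPG values the diary must contain are those belonging to episodes the subject has already recorded, so a search of it for unreported lows has little left to find. The reporting duty is unchanged, but its written check has lost its data source.

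At stake are the counts and rates of hypoglycaemic episodes in Section 10.3.2.1, a supportive secondary endpoint presented descriptively by cohort and treatment. An unreported low reading would also not trigger the question on severity or the re-training. Severe episodes count towards the escalation decision in Section 8.1.1, although this question is only a back-up route to them.

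**Working it through.** The check is a comparison of texts, plus a count of the values affected. The plan states no figure to reproduce.

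**1. Where a calibration reading is held**

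| | Protocol version 2.0 | After Amendment 4 |
|---|---|---|
| Diary | date, time, value | date, time |
| BG meter download | not mentioned | date, time, value |
| CRF | transcribed from the diary | entered from the download |
| Source named for the low-value search (Appendix 7) | diary | diary (not changed) |

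The values are not lost. Only the instruction to screen them is missing.

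**2. Which readings fall in the gap.** A low reading that the subject reports as an episode still reaches the diary. The gap is confined to low readings the subject does not report: calibration readings, and any other meter reading not tied to a reported episode.

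**3. Which summaries are exposed.** Under Appendix 7, missing symptom information is classified as no symptoms, and missing self-treatment information as able to self-treat.
- An unreported reading at or below 70 mg/dL would therefore normally be an ADA asymptomatic episode.
- The Novo Nordisk asymptomatic category requires a value below 56 mg/dL. A self-treated reading from 56 to 70 mg/dL is unclassifiable in that system.
- The under-count would thus fall mainly on ADA asymptomatic episodes.

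**4. What is not exposed.** The primary endpoint (time below 54 mg/dL), the corresponding escalation criterion and the low-glucose derivations in Table 10-1 all use interstitial glucose from the CGM.

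**5. Number of values to review**
- Frequency: "CGM sensor should be calibrated twice daily" (Section 9.10).
- Days per period: 7, or 6 if the flowchart's -1 day visit window is used.
- Calibration values per subject per visit: 2 × 7 = 14, or 2 × 6 = 12.
- Subject-visits (visits 3 and 4): 24 × 2 = 48 if all three cohorts of 8 open and all subjects complete, or 8 × 2 = 16 if only cohort 1 opens.
- Calibration values over the whole trial: at most 48 × 14 = 672.

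These counts measure the size of the review, not the number of missed lows. The documents give no rate of low or unreported readings, and none is assumed here.

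**The case against.** The strongest reply is that the gap needs a lapse by the subject first. A calibration reading at or below 70 mg/dL is itself a reportable episode, and Amendment 4 keeps diary reporting for episodes. That is right, but the Appendix 7 check exists for exactly that lapse.

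A second reply is that staff see every calibration value when they match the download to the diary times and enter it in the CRF, at the same visits at which hypoglycaemic episodes are recorded. Monitors also check source data for omissions, and plasma glucose entered in the iLet is transferred to the sponsor's database. Amendment 4 even captures values that a subject would never have written down. All this reduces the likely effect, but none of these steps tells anyone to screen for values at or below 70 mg/dL or to question the subject.

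Third, naming the diary does not forbid using other sources. True, but it is the only source named. A site source document agreement (Appendix 3) might name another, but it is not among the documents.

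Some points stand:
- The readings that Amendment 1 adds after inadvertent acetaminophen use, where staff "instruct the subject to measure BG using the BG meter to verify CGM readings as frequently as needed", are a weak example of unseen lows, because staff direct those checks and compare the results with the CGM.
- A severe episode is unlikely to surface only through an unreported calibration reading, given 24-hour remote monitoring and the reporting of severe episodes as SAEs.
- Subjects are blinded to the order of settings and both periods follow the same procedure, so there is no evident reason for bias between settings.

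**Conclusion.** The concern holds, as a minor inconsistency. Two provisions in force no longer fit together: Amendment 4 redirects the calibration values to the meter download but not the safety review that relied on them. The consequence is a possible under-count of unknown size in a supportive, descriptive endpoint, mainly ADA asymptomatic episodes.

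The conclusion rests on the changes the four amendments list, because the consolidated protocol after Amendment 4 and the modified diary are not among the documents. Confidence is high that the texts do not match. How many low readings would be missed in practice cannot be judged from the documents.

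**What to change.** Amend the Appendix 7 sentence so that at each site visit the investigator reviews the BG meter download as well as the diary for SMPG values at or below 3.9 mmol/L (70 mg/dL) not reported as hypoglycaemic episodes. Values found would be handled under the existing Appendix 7 procedure, including the 60-minute rule for what counts as one episode. The sentences on late forms and re-training name no source and can stay as they are.

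The cost is one sentence and some staff time. The meter is already downloaded at every site visit, so the added work is reading through one subject's values at each of at most 48 subject-visits, probably a few minutes each (an estimate; the documents give no timing). The change concerns data review only and alters no clinical rule.

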Appendix 8 Country-specific requirements

There is no country specific requirement applicable for US in this trial.

Faster-acting insulin aspart
Trial ID: NN1218-4360
Clinical Trial Report
Appendix 16.1.1

~~CONFIDENTIAL~~

Date:
Version:
Status:

25 October 2019
1.0
Final

Novo Nordisk

Global and country key Novo Nordisk staff

Attachments I and II (if applicable) to the protocol are located in the Trial Master File.

Content: Global key staff and Country key staff

Protocol Amendment

no 1

**to Protocol, version 2
dated 07 June 2018**

Trial ID:NN1218-4360

**An Exploratory Trial investigating the Safety and Efficacy of Fast-acting Insulin Aspart in a
Closed-loop Insulin Delivery System (bionic pancreas) in Adults with Type 1 Diabetes**

**Trial phase: 2
Applicable to all countries**

~~This confidential document is the property of Novo Nordisk. No unpublished information contained herein may be disclosed without prior written approval from Novo Nordisk. Access to this document must be restricted to relevant parties.~~

Table of Contents

1	Introduction including rationale for the protocol amendment.....	3
2	Changes to protocol	3
3	Changes to subject informed consent	11

1 Introduction including rationale for the protocol amendment

This protocol amendment will serve to address the comments raised by the health authorities, specifically the US Food and Drug Administration (FDA) comments received during the Investigational Device Exemption (IDE) review.

The changes are mainly related to safety of the subject.

In this protocol amendment:

- Any new text is written *in italics*.
- Any text deleted from the protocol is written using ~~strike through~~.

Protocol has been amended to include the following major changes:

- Addition of exclusion criteria related to the use of acetaminophen
- Extension of “in-patient” period to 2 days
- Addition of individual subject’s discontinuation criteria
- Addition of trial stopping criteria
- Addition of further instructions for subjects in case of a hyperglycaemia or hypoglycaemia

A number of inconsistencies has been found and corrected and minor clarifications have been added. The subject informed consent has been updated accordingly to the changes implemented.

2 Changes to protocol

Section 1.2.2: Key exclusion criteria

- *Unwilling or unable to avoid acetaminophen throughout the trial*

Section 2: Flowchart

Footnote

h) Subject will spend ~~the 1st-2~~ nights at a hotel for close observation during each treatment period and each cross-over visit

Section 5.1: Overall Design

For each subject, an ‘in-patient’ period is implemented for the first ~~± 2~~ days (~~4824~~ hours ~~± 3 6~~ hours) following treatment initiation, i.e. at visit 2 and at cross-over visit (visit 3). This entails that subjects will stay at a designated place (such as a hotel) for the specified duration and will be discharged *following as per PI’s evaluation discretion*, see section 9.15. This period is included in the 7 days treatment period. The ‘out-patient’ period is defined as the period after the discharge

from the designated place where the subject stays during the ‘in-patient’ period and until the end of treatment. *During the ‘in-patient’ period, subjects will be allowed to leave the designated place during the day but they will be restricted to the area immediately surrounding the designated place (e.g. within 15mins walk).*

[figure not shown]

Figure 5-2 In-patient and Out-patient period

Each treatment period will have 24 days of “in-patient” period and 56 days of “out-patient” period, see Figure 5–2.

Section 6.2: Exclusion criteria

16. Unwilling or unable to avoid acetaminophen throughout the trial

Section 7.1.1: Investigational and non-investigational medicinal products

Table 7-1 Trial products provided by Novo Nordisk A/S

Trial product name:	Fast-acting insulin aspart , 100 U/ml (Investigational medicinal product (IMP), test product)	Fiasp® , 100 U/ml(Non-Investigational medicinal product (NIMP))
Dosage form:	Solution for injection	(Non-Investigational medicinal product (NIMP))
Route of administration:	Subcutaneous	Solution for injection
Dosing instructions:	Dosing is handled by iLet™ autonomously	Subcutaneous
Packaging	1.6 mL cartridge (PumpCart®)	Dosing as per PI's discretion

Section 7.1.2: Medical devices

Investigational medical device(s):

Beta Bionics will provide the iLet™ and the StudyPhone with CGM application (app). For complaints related to the iLet™, the investigator should report it to both Novo Nordisk and Beta Bionics, see Appendix 6. And for complaints related to the Study phone *and the apps*, the investigator must contact Beta Bionics directly.

Non-investigational medical device(s):

- CGM device (Dexcom G5®) and its auxiliaries
- StudyPhone with CGM app (*Dexcom G5® and CGMRelay app*)**
- *Remote Monitoring app (iLet-RM)*
- BG meter (Contour® Next One) and its auxiliaries
- Infusion set with 60 cm tube (Contact™ detach)
- *Blood ketone meter (Precision Xtra®) and its auxiliaries*

Novo Nordisk will provide the aforementioned non-investigational medical devices (except StudyPhone with CGM app and *Remote Monitoring app*) to the subjects along with the paper diary.

For complaints related to the BG meter, *ketone meter*, infusion set or CGM device, the investigator must contact the device manufacturer's technical support according to Operator's Manuals provided with the BG meter, *ketone meter*, infusion set and the CGM device.

Training in the medical devices

iLet™

- How to replace the PumpCart®
- How and when to replace the batteries
- Troubleshooting in case of iLet™ failure or any technical problems
- *How to react in case of an alarm*

CGM – Dexcom G5®

- How and when to change the sensor
- How and when to calibrate the sensor
- How to use the CGM app on StudyPhone
- *How to react in case of an alarm*

BG Measurement - Contour® Next One

- When to perform self-measured plasma glucose (SMPG) measurements
- How and where to report the SMPG measurements
- ~~How and when to perform ketone measurement~~

Ketone measurement - Precision Xtra®

- *How and when to perform ketone measurement*

Section 7.8: Treatment after the end of the trial

When discontinuing trial product, the subject should be transferred *back to the insulin a suitable marketed product that was used for CSII therapy prior to the initiation of the trial at the discretion of the investigator.*

Section 8.1: Discontinuation of trial treatment

The subject must be discontinued from trial treatment, if the following applies:

5. *≥2 episodes of severe hypoglycaemia (see Appendix 7 for definition), possibly/probably related to investigational medicinal product and/or investigational medical device*

6. *Diabetic ketoacidosis possibly/probably related to investigational medicinal product and/or investigational medical device*

8.1.4: Trial stopping criteria

If any of below listed criterion are met, then the PI must suspend the further treatment of all subjects via the iLet™ and communicate the same to Novo Nordisk within 24 hours. Novo Nordisk safety committee will then evaluate the need for further investigation and makes the final decision on stopping the trial. All subjects must be transitioned to their usual CSII treatment until the final decision on stopping the trial has been made.

- *≥3 subjects experience any serious adverse events possibly/probably related to investigational medical device*
- *≥3 subjects experience any severe hypoglycaemic episodes (see Appendix 7 for definition) possibly/probably related to investigational medical device*
- *≥3 subjects experience any diabetic ketoacidosis possibly/probably related to investigational medical device*

Section 9.2.1: Time period and frequency for collecting AE and SAE information

Table 9-1 AEs requiring additional data collection (via specific event form)

Event type	AE requiring additional event form
Hypoglycaemic episode ^a	X
Infusion site reaction ^b	X
Medication error ^c	X

^a Non-serious hypoglycaemic episode should only be reported on the hypoglycaemic episode form. *All severe hypoglycaemic episodes are qualified as SAEs and should be reported on the AE form, SIF and Hypoglycaemic episode form. Refer to Section 9.2.6 and Appendix 4 for reporting details*

Section 9.2.6: Disease-related events and/or disease-related outcomes not qualifying as an AE or SAE

Hypoglycaemia

Hypoglycaemic episodes should follow the below reporting:

- Non-serious hypoglycaemia must be reported on a hypoglycaemic episode form.
- *All severe hypoglycaemic episodes are qualified as SAEs and should be reported on a hypoglycaemic episode form, an AE form and a safety information form. One AE form and*

safety information for m can cover several hypoglycaemic episode forms, if the subject has not recovered between the episodes. *Severe hypoglycaemic episodes should follow the same reporting timelines as SAEs.*

~~If the hypoglycaemic episode fulfils the criteria for an SAE then in addition to the above, an AE form and a safety information form must also be filled in.~~

Section 9.5.1: Change of infusion set

Infusion sets must be replaced if any change in the insulin solution or occlusion is perceived by the subject, e.g. because of an iLet™ alarm indicating an occlusion or other observations pointing towards obstruction of the insulin flow. *Infusion sets should also be changed in case of prolonged hyperglycaemia and if the ketone measurement is positive.* Infusion set changes can be considered as a ‘non-routine change’ or ‘routine change’.

Section 9.10: Continuous glucose measurement

Subjects should be instructed to avoid medications with acetaminophen/paracetamol while wearing the CGM sensor. These medications may affect the performance and readings of the CGM sensor (e.g. false high CGM readings)⁷⁻⁹. *If a subject inadvertently takes acetaminophen during the trial, they will be instructed to contact study staff. Site staff will closely monitor their CGM readings and instruct the subject to measure BG using the BG meter to verify CGM readings as frequently as needed. If the BG is closely correlated with the subject’s CGM glucose, study staff will continue to monitor closely. If CGM glucose is consistently higher than BG by >20 mg/dL(1.1 mmol/L) for BG ≤100 mg/dL (5.55 mmol/L) or >20% for BG >100 mg/dL(5.55 mmol/L), then the study staff may temporarily discontinue the iLet™ for the duration of action of the acetaminophen.*

Also, subject should be instructed to remove the Dexcom G5 sensor, transmitter, and receiver before x-ray, Magnetic Resonance Imaging (MRI), Computed Tomography (CT) scan, or high-frequency electrical heat (diathermy).

Section 9.13: Back-up Kits

- ~~Fiasp® FlexTouch® pen injector (supplied by Novo Nordisk)~~
- ~~Needles (to be used with Fiasp® pen injector FlexTouch®)~~
- ~~Urine sticks for ketone monitoring~~

Subjects will also be encouraged to always carry the BG - meter, *Ketone meter* and test strips.

Section 9.15: Discharge criteria

The discharge of subjects from the “in-patient” period (during which subjects will be at a designated place such as a hotel) is at the discretion of the PI. In order to make the evaluation whether it is safe for the subjects to continue to the “out-patient” period of the trial, the PI may rely on data that include but are not limited to: hypoglycaemic episodes, the number of times carbohydrates are taken by subjects to prevent or treat hypoglycaemic episodes and time in low interstitial glucose (defined as < 54 mg/dL; 3 mmol/L). *Subjects will not be discharged if they have any severe hypoglycaemic episode possibly/probably related to investigational medicinal product and/or investigational medical device in the last 24 hours.*

In the event of diabetic ketoacidosis or ≥ 2 episodes of severe hypoglycaemia, possibly/probably related to investigational medicinal product and/or investigational medical device, the subject will discontinue the trial treatment as per section 8.1.

Section 9.16: Remote Monitoring

An alert will be generated *after 15 minutes* if remote monitoring for a subject goes offline. *Site staff will contact the subject to troubleshoot the issue and will ask subject to replace the sensor if it is not possible to recover the sensor and/or connectivity within 20-30 minutes.* Site staff will call the subject every 2 hours to check on safety and device function until remote monitoring is restored. If there are no indications of device malfunction as the cause for lost connectivity, the glucose level is in safe range, and a subject chooses to remain in an area with poor network coverage, site staff will instruct the subject to check the iLet™ display or the CGM app (*Dexcom G5®*) on the study phone at least every 20 minutes for alert icons and to be aware that we are unable to monitor for severe lows or highs at this time. *If the subject is unable to establish the CGM connectivity after 6 hours, they should transition to their usual CSII treatment until the Site staff can assess the functionality of the device and the subject’s ability to use it in person.*

Section 9.16.1: Remote Monitoring for Hypoglycaemia

Site staff will verify that the subjects, or their designated contacts, are aware of the hypoglycaemia and are taking action to treat it. Subjects will be reminded of the procedures to follow in case of hypoglycaemia and the site staff will ensure they understand and will follow the procedures. *Subjects will be instructed to measure BG in response to an alarm to verify the CGM reading. If the BG measurement confirms hypoglycaemia, the subjects will be instructed to treat with 15 grams of rapid acting carbohydrates and check the BG again in 15 mins. Subjects will be instructed to treat with another 15 grams of rapid acting carbohydrates if they are still hypoglycaemic. Subjects will be instructed to continue to monitor BG until it returns to ≥ 70 mg/dL (3.9 mmol/L).* Subjects will be encouraged to follow up with any questions or concerns. All contact with the subjects in response to hypoglycaemia alarms will be documented in the subjects’ medical records.

Section 9.16.2: Remote Monitoring for Hyperglycaemia

Subjects will be reminded to contact the site immediately in case they have been hyperglycaemic for ≥ 2 hours. Site staff will recommend the subjects to measure BG and ketones every hour until the BG is < 180 mg/dl (10 mmol/L) and the ketones measurement is negative. *If ketone measurement is positive (≥ 0.6 mmol/L), they will be instructed to change their infusion set immediately. If ketones measurement is negative (< 0.6 mmol/L), they will be instructed to inspect their infusion set and the iLet™ for proper functioning, and consider replacing the infusion set if they are suspicious it has failed.* Subjects will be encouraged to follow up with any questions or concerns. All contact with the subjects in response to a hyperglycaemia alarms will be documented in the subjects' medical records.

